### Patient Exclusion:

- 1. Inability to provide informed consent prior to randomization
- 2. Anatomy requiring coronary artery bypass surgery (CABG)
- 3. History of prior CABG in the territory of the vessel being considered for PCI
- 4. Heavily calcified lesion requiring rotablation or other debulking or scoring device for successful stent deployment
- 5. Large thrombus burden on angiography
- 6. Previously stented vessels.
- 7. Ostial lesions: lesion located within 5mm of the origin of the LAD, LCx, or RCA
- 8. Lesions at bifurcations and those that occlude side branches>2.5mm
- 9. Recent (<72 hours) ST-elevation myocardial infarction (STEMI)
- 10. Planned surgical procedures in the subsequent 12 months
- 11. History of hypersensitivity or contraindication to device materials and their degradants, everolimus, zotarolimus, cobalt, chromium, nickel, platinum, tungsten, acrylic and fluoro polymers
- 12. History of any solid organ transplantation or subject is on a waiting list for any solid organ transplant.
- 13. Left ventricular ejection fraction < 30%
- 14. Known allergies to clinically utilized anti-thrombotic or anti-platelet agents
- 15. Unable to tolerate long term dual anti-platelet therapy
- 16. Pregnancy or lactation

- 17. Subject has renal insufficiency as defined as an estimated GFR < 30 ml/min/1.73m^2.
- 18. Concurrent enrollment in another clinical trial that has not yet completed its primary endpoint

#### **Study Endpoints**

#### Primary Endpoints (Efficacy):

1. In stent mean cross-sectional area of neo-intimal tissue coverageby OCT at follow-up.

#### Secondary Endpoints:

#### A. In-Stent

- 1. Safety: Mean thickness of strut coverage at follow up
- 2. Mechanistic:
  - a. Degree of vascular straightening post-PCI (post PCI angulation -baseline angulation)
  - b. Plaque prolapse post-PCI (identified by OCT)
  - c. Percent stent area with low WSSpost-PCI (OCT derived)

#### B. Stent Edge (5 mm proximal and distal to stent)

- 1. Efficacy: Change in plaque area at follow up
- 2. Mechanistic:
  - a. Degree of vascular straightening post-PCI at the stent edges
  - b. Percent area with low WSS at stent edges post-PCI (IVUS derived)

Figure 4: Schema of Study endpoints

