### 2. Angiographic assessment of angulation

Angulation is the angle created by the intersection of two tangential lines at the beginning and end of an index coronary segment with the angiogram frozen in end-diastole. In this study, we define an angulated vessel as one with ≥30degrees bend (Figure 3). When the angulation is clearly >60 degrees, a visual assessment by the investigator will suffice for enrollment. However, for angles <60 degrees the angiographic image is frozen in end diastole in the control room and printed on paper. Subsequently, 2 tangential lines are drawn on the vessel at the proximal and distal edge of the lesion and the intersecting angle measured with a protractor. In cases where the affected artery/stent has more than one curvature (assumes an "S" shape, instead of variations of a "C" shape), the

Figure 3: Angulation

higher degree of angulation will be analyzed. Stents that overlap or are in very close proximity to each other with a gap of less than 5 mm will be assigned to the same

coronary lesion.

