#### 4. Wall Shear Stress Calculations

Computational fluid dynamic (CFD) simulations to calculate WSS values have been used extensively and validated in our laboratory. Following angiographic, IVUS and OCT acquisition, 3-dimensional (3D) coronary geometries will be reconstructed by determining the location of the OCT transducer during pullback by using the corresponding angiographic projections. The 3D reconstructed catheter core serves as the stem on which to rebuild the 3D geometry. Following image adjustment due to rotation, each frame is aligned perpendicular to the catheter core. Lumen boundary points for each frame will be determined connected by spline curves to connect consecutive images. The geometry is smoothed, meshed, and imported into the commercial solver (Ansys, Inc., Canonsburg, PA), which employs the finite volume method for solving the Navier-Stokes equations. Velocity profiles will be applied at the inlet, traction-free boundary conditions are applied at all outlets, and a no-slip boundary condition (v = 0) is applied at the wall. The fluid (blood) is assumed to be an incompressible Newtonian fluid, which is valid under the pulsatile, moderate Reynolds number flow conditions in coronary arteries. WSS values are determined as a function of time in the cardiac cycle and the evaluation is highly reproducible.

Nodal WSS values will be extracted from the area of interest (i.e., lesion/stented region and stent edges) of computational models at pre- and post-stenting. The stented region and 5-millimeter (mm) segments of the proximal and distal edges will be divided into 1- mm segments and WSS values will be spatially and temporally averaged. Low WSS will be defined as <10 Dynes/cm^2. Corresponding regions between the pre-and post-stenting models for a given patient will be examined to assess alterations in WSS following stent implantation. Arterial straightening will be assessed by examination of the OCT-derived coronary reconstructions. Following reconstruction, centerline data will be examined to quantify vessel curvature, average cross-sectional area, maximum/minimum/average lumen diameters, and vessel volume will be calculated.

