#### **Statistics**

OCT cross-section frames will be selected from the stented segments at approximately 1 mm intervals for quantitative analysis. Each observed stent strut in each still frame will be classified as either completely or incompletely tissue-covered. Furthermore, in those struts where tissue coverage is observed, tissue coverage area and tissue coverage thickness will be measured. Previously published studies investigating R-ZES and X-EES strut re-endothelialization by OCT in all comers did not show statistically significant differences in neointimal thickness or volume, though the studies did not concentrate on angulated vessels. In a sample of 58 patients (30 ZES and 28 EES) with 72 lesions, 107stents, and 23,197 struts, the OCT sub-study of the RESOLUTE All Comers OCTtrial showed the tissue coverage volume of 15.9mm^3±11.6mm^3 for the ZES and 18.7mm^3±14.4mm^3 for EES (p-value=0.27).Power calculations were based on the assumption that at 12 months the tissue coverage volume for ZES was 14.68mm^3and EES 22mm^3. Detection of a 20% or more change in primary endpoint between the two groups at a power of 80% and a two-sided alpha level of 0.05 will requires an enrollment of 50 patients per group. Assuming a dropout rate of 20%, we propose to recruit 126 patients.

Continuous variables will be reported as mean and standard deviations (1SD), and a t-test or U-test will be employed depending on whether or not the variables are normally distributed and the standards of deviations are the same. Analysis of variables at the level of patient, treatment arm, and lesion will be performed using multilevel regression models. Chi-square test or Fisher's exact test will be used, as appropriate, to compare categorical variables.

All statistical analyses will be carried out using the Statistical Package for Social Sciences (SPSS) software (SPSS, Inc., Chicago, IL). A two-sided *p*-value of <0.05 will be considered statistically significant.

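### No baseline adjustment is specified for post-PCI percent low wall shear stress, although the pre-stent value is already computed; straightening would also gain from ANCOVA

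*Combined protocol and SAP*

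**What the plan says.** Under Secondary Endpoints, the stent-edge mechanistic list includes "Percent area with low WSS at stent edges post-PCI (IVUS derived". The in-stent list has the equivalent OCT-derived percentage. Both refer to the post-PCI model only. In-stent straightening is a change score: "Degree of vascular straightening post-PCI (post PCI angulation -baseline angulation". The stent-edge straightening endpoint has no formula of its own.

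The pre-stent counterpart of the WSS endpoints exists. Section 4, Wall Shear Stress Calculations, states: "Nodal WSS values will be extracted from the area of interest (i.e., lesion/stented region and stent edges) of computational models at pre- and post-stenting". The use it gives for the pre-stent values is a within-patient look at how shear changes after implantation. The Design section schedules both IVUS and OCT before deployment and says that patients will be stratified by diabetes.

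For continuous variables, the Statistics section says that "a t-test or U-test will be employed depending on whether or not the variables are normally distributed". It then adds multilevel regression at patient, arm and lesion level, without saying which outcomes are modelled or which covariates enter. It mentions neither pre-stent WSS, baseline angle nor the diabetes stratum.

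**The concern.** In the Hypotheses section, less straightening and fewer low-WSS areas are the first links in the chain from stent design to tissue coverage and edge plaque. If a patient's low-WSS percentage after PCI is partly predictable from the percentage before PCI, a test on the post-PCI value alone leaves that predictable variation in the error term. It also leaves any chance imbalance between arms uncorrected.

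The edges are where this matters most. They are the 5 mm segments outside the stent, so vessel size and flow there may carry over from the pre-stent to the post-stent model. Within the stent, the lumen itself is changed, so the carry-over may be weaker. At stake is the precision of the mechanistic comparison, and the freedom to choose covariates after the data are seen if the regression stays unspecified.

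**Working it through.** **Which N applies.** The plan's size calculation is for the primary endpoint, "at a power of 80% and a two-sided alpha level of 0.05". The assumed volumes are 14.68 and 22 mm³, a difference of 7.32 mm³. The power statement gives no SD; the quoted OCT sub-study gives 11.6 (30 patients) and 14.4 (28 patients).

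- Pooled SD = √[(29 × 11.6² + 27 × 14.4²)/56] = 13.03.
- n per arm = 2 × [13.03 × (1.960 + 0.842)/7.32]² = 49.7, so 50. The plan's figure is reproduced. (The root mean square SD of 13.08 gives 50.09, so 51.)
- 50/0.8 = 62.5, so 63 per arm and 126 in all.

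The Design section applies the 20% loss to the 1-year invasive visit and expects 126 patients to complete baseline evaluation. Post-PCI shear and angle are measured at the index procedure, so up to 63 per arm is the relevant number.

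**Low WSS.** Let ρ be the within-arm correlation between the pre-stent and post-PCI percentages. It is not in the documents, so a range is assumed. In a linear model:

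- Residual variance with ANCOVA = (1 − ρ²) × post-PCI variance.
- Unadjusted detectable difference at 80% power, two-sided 0.05 = (1.960 + 0.842) × √(2/63) = 0.50 SD.
- Adjusted detectable difference = 0.499 × √(1 − ρ²).

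| Assumed ρ | Variance reduction | Detectable difference (SD), 63 per arm | Power where the unadjusted test has 80% |
|---|---|---|---|
| 0 | 0% | 0.50 | 80% |
| 0.2 | 4% | 0.49 | 81.6% |
| 0.3 | 9% | 0.48 | 83.6% |
| 0.5 | 25% | 0.43 | 89.9% |
| 0.7 | 49% | 0.36 | 97.5% |

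**Straightening.** The planned outcome is already a difference from baseline. With equal SDs before and after PCI (assumed):

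- Change-score variance = 2(1 − ρ) × post-PCI variance.
- ANCOVA variance = (1 − ρ²) × post-PCI variance.
- Ratio of ANCOVA to change score = (1 + ρ)/2.

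| Assumed ρ | Ratio | Variance saved | Power where the change score has 80% |
|---|---|---|---|
| 0.5 | 0.75 | 25% | 89.9% |
| 0.7 | 0.85 | 15% | 86.0% |
| 0.8 | 0.90 | 10% | 84.0% |

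**The case against.** The strongest reply is that nothing here is invalid. Randomisation makes the unadjusted comparison unbiased, these are secondary mechanistic endpoints with no stated power, and the plan does name a regression. That stands as far as it goes: this is a matter of efficiency. The regression sentence, however, lists no outcome and no covariate, so it does not pre-specify baseline adjustment.

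The second reply is that the gain is unknown. This also stands. Eligible patients have a severe lesion, and treating it may alter flow. Section 4 does not say whether the same inlet velocity profile is used before and after stenting. If ρ is only 0.2–0.3, the saving is 4–9% of variance. A further fair point is that a percentage below a threshold is bounded and may be skewed, so the linear-model figures are approximate.

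Three stronger readings are tempting, and the documents do not support them:

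- **That baseline angle goes unused.** The straightening endpoint subtracts it; only the step from change score to ANCOVA is missing.
- **That some patients will have no numeric baseline angle**, because "When the angulation is clearly >60 degrees, a visual assessment by the investigator will suffice for enrollment". That rule governs enrolment only. The endpoint cannot be computed without a baseline angle, and Section 4 provides for straightening to be assessed from the OCT-derived reconstructions.
- **That the primary endpoint needs baseline angle as a covariate.** Nothing in the documents indicates how strongly the angle predicts tissue coverage.

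**Conclusion.** The point holds as an efficiency improvement. No baseline adjustment is specified for percent low WSS at the edges or in the stent, although the matching pre-stent value and the diabetes stratum are both available. The gain ranges from minor (4% of variance at a correlation of 0.2) to substantial (49% at 0.7), and is likelier to be worthwhile at the edges than in the stent. For straightening, the further gain over the planned change score is about 10–25% of variance.

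These figures rest on assumed correlations, linear models and, for straightening, equal SDs before and after PCI. They apply to up to 126 patients. A reader might take 100 from the sample-size text, but that is the 1-year count. Nor should the point be read as a flaw in validity, or as affecting the stated 50 per group or the primary analysis.

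**What to change.** Add to the Statistics section:

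- **Percent low WSS (edge and in-stent, separately):** ANCOVA, or the multilevel model already named, of the post-PCI value on arm, the pre-stent value for the same region from the same imaging modality, and diabetes stratum. State a transformation or rank-based version to be used if residuals are clearly non-normal.
- **Straightening:** post-PCI angle on arm, baseline angle measured by the same method, and diabetes stratum. The protocol describes both an angiographic tangent angle and reconstruction-based curvature, so name the one that defines the endpoint.
- **Missing pre-stent models:** keep patients who have a post-PCI value but no usable pre-stent model, for example by setting the covariate to its overall mean, calculated without regard to arm.

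The cost is SAP wording, the rule for missing covariates, and about one degree of freedom per covariate out of roughly 124 (126 − 2). No additional imaging is needed, and the sample size does not change.

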#### **Statistics**

OCT cross-section frames will be selected from the stented segments at approximately 1 mm intervals for quantitative analysis. Each observed stent strut in each still frame will be classified as either completely or incompletely tissue-covered. Furthermore, in those struts where tissue coverage is observed, tissue coverage area and tissue coverage thickness will be measured. Previously published studies investigating R-ZES and X-EES strut re-endothelialization by OCT in all comers did not show statistically significant differences in neointimal thickness or volume, though the studies did not concentrate on angulated vessels. In a sample of 58 patients (30 ZES and 28 EES) with 72 lesions, 107stents, and 23,197 struts, the OCT sub-study of the RESOLUTE All Comers OCTtrial showed the tissue coverage volume of 15.9mm^3±11.6mm^3 for the ZES and 18.7mm^3±14.4mm^3 for EES (p-value=0.27).Power calculations were based on the assumption that at 12 months the tissue coverage volume for ZES was 14.68mm^3and EES 22mm^3. Detection of a 20% or more change in primary endpoint between the two groups at a power of 80% and a two-sided alpha level of 0.05 will requires an enrollment of 50 patients per group. Assuming a dropout rate of 20%, we propose to recruit 126 patients.

Continuous variables will be reported as mean and standard deviations (1SD), and a t-test or U-test will be employed depending on whether or not the variables are normally distributed and the standards of deviations are the same. Analysis of variables at the level of patient, treatment arm, and lesion will be performed using multilevel regression models. Chi-square test or Fisher's exact test will be used, as appropriate, to compare categorical variables.

All statistical analyses will be carried out using the Statistical Package for Social Sciences (SPSS) software (SPSS, Inc., Chicago, IL). A two-sided *p*-value of <0.05 will be considered statistically significant.

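### The plan claims 80% power for a 20% difference, but 50 per group matches its assumed 33% difference in volume; on those inputs power for 20% is about 20–38%

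*Combined protocol and SAP*

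**What the plan says.** The Statistics section cites an earlier OCT sub-study, "In a sample of 58 patients (30 ZES and 28 EES) with 72 lesions", with tissue coverage volumes of "15.9mm 3 ±11.6mm 3 for the ZES and 18.7mm 3 ±14.4mm 3 for EES". It then states the planning assumption, that "at 12 months the tissue coverage volume for ZES was 14.68mm 3 and EES 22mm 3". The next sentence promises "Detection of a 20% or more change in primary endpoint between the two groups at a power of 80" per cent, and says that "a two-sided alpha level of 0.05 will requires an enrollment of 50 patients per group". Allowing for 20% dropout, 126 patients are to be recruited; the Design section expects 100 to complete follow-up.

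The primary endpoint, under Primary Endpoints (Efficacy), is "In stent mean cross-sectional area of neo-intimal tissue coverageby OCT at follow-up". Section 3.2.2 derives it as stent area minus lumen area. It is therefore an area, whereas every figure in the power paragraph is a volume.

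**The concern.** Two adjacent sentences give different effect sizes for one sample size. The assumed means are 33% apart relative to EES and 50% apart relative to ZES. They are not 20% apart on either base, and seeing this needs no SD. The 20% claim is also made for the primary endpoint (area), although the inputs are volumes.

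This is the only justification of the sample size. If the 20% claim is taken at face value, a null result would be read as evidence against a difference of that size. Readers also cannot tell which effect, SD and endpoint the 50 per group was planned for.

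**Working it through.** **Inputs from the documents.** Means 14.68 and 22 mm³; SDs 11.6 (ZES, 30 patients) and 14.4 (EES, 28 patients); two-sided alpha 0.05; power 80%; 1:1 allocation; 50 evaluable per group; 20% dropout.

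**Inferred input.** The plan gives no planning SD, so I combine the two cited SDs:

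- Root mean square: √[(11.6² + 14.4²)/2] = √170.96 = 13.08 mm³.
- Weighted by degrees of freedom: √[(29 × 11.6² + 27 × 14.4²)/56] = 13.03 mm³.

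**Step 1: size of the assumed difference.** 22 − 14.68 = 7.32 mm³. 7.32/22 = 33.3%; 7.32/14.68 = 49.9%.

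**Step 2: reproduce the plan's number.** n per group = 2(1.960 + 0.842)² × SD²/Δ².

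- SD 13.08, Δ 7.32: n = 50.1.
- SD 13.03, Δ 7.32: n = 49.7.
- Dropout: 50/0.8 = 62.5, rounded up to 63; 2 × 63 = 126.

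The 50 and the 126 both reproduce, using the 33% difference in volume.

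**Step 3: the same inputs with a 20% difference.** The plan does not say 20% of what, so each base is shown. Power is from the noncentral t distribution at n = 50 per group and SD 13.08; n is from the formula in Step 2.

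| Difference (mm³) | Base | Power at 50 per group | n per group for 80% |
|---|---|---|---|
| 7.32 | plan's means (33% of EES) | 79% | 50.1 |
| 4.40 | 20% of 22 | 38% | 138.6 |
| 3.74 | 20% of 18.7 | 29% | 191.9 |
| 3.18 | 20% of 15.9 | 23% | 265.4 |
| 2.94 | 20% of 14.68 | 20% | 311.3 |

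**Step 4: sensitivity.**

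- Taking one arm's SD alone (11.6 or 14.4), power is 47% or 33% for 4.40 mm³, and 24% or 17% for 2.94 mm³.
- A Welch test simulated with unequal SDs of 11.6 and 14.4 (100,000 runs) gives 79%, 38%, 29% and 20% for 7.32, 4.40, 3.74 and 2.94 mm³.
- On the log scale, with coefficients of variation of 0.73 to 0.77, power for a 20% reduction is 37–40%.
- No 20% variant tried returns 50 per group. The smallest n, one-sided with SD 11.6 and 20% of 22, is 86.

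**Step 5: what 50 per group can detect on any scale, including area.** With 80% power the smallest detectable difference is 0.566 SD. On the volume scale that is 0.566 × 13.08 = 7.40 mm³, or 33.6% of 22. A 20% difference is detectable only if SD/mean ≤ 0.20/0.566 = 0.353. The cited volume data have 11.6/15.9 = 0.73 and 14.4/18.7 = 0.77. The documents give no such ratio for area. As an assumed range, ratios of 35%, 50%, 60% and 77% give power of 81%, 51%, 38% and 25%.

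**The case against.** **The SD is inferred.** This is true, and it is the main limit on the percentages. The mismatch between 33% and 20% does not depend on it, and the power for 20% stays below 50% with either cited SD.

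**The SDs may not be patient-level.** The sub-study had 107 stents in 58 patients and reports p = 0.27. A Welch test on the printed means and SDs gives p = 0.42 with 30 and 28 patients, but 0.27 with an assumed 54 and 53 stents. The SDs may therefore be per stent, or the p-value may come from a clustered model. This trial also limits inclusion to lesions treatable with a single stent, so its spread in volume may differ. This objection stands as a reason to confirm the unit. It does not rescue the claim: 50 per group for 20% of 22 would need an SD near 7.8 mm³, well below both cited values.

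**The phrase covers 20% or more, which includes 33%.** As a statement of detectable effect it sets 20% as the minimum, and power is lowest at the minimum.

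**20% of the EES mean is the natural base.** This is fair. EES is the comparator and the hypothesis is less tissue with R-ZES. The best single figure is then 38%; the 20% figure comes from using the ZES mean as base.

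**Area may vary less than volume.** It may. For area the 20% claim is unsupported rather than shown to be wrong, because the documents give no mean or SD for it.

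**The sample size itself reproduces.** It does. The 50 and the 126 are not in dispute.

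**Conclusion.** The point holds. On the plan's own volume figures, 50 per group gives about 79% power for the assumed 7.32 mm³ difference, but only about 38% for 20% of the EES mean, falling to 20% for 20% of the ZES mean. A true 20% difference in volume would be missed about 62–80% of the time, not 20%. These percentages assume that the cited SDs are the planning SDs and apply at patient level. That is an inference, supported by the near-exact return of n = 50. For the primary endpoint of mean area, power for a 20% difference cannot be computed from the documents. The sentence needs correcting because it is the sole justification of the sample size.

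**What to change.** First, the sponsor should confirm the SD used in planning and whether it is per patient, lesion or stent. If it is the cited SD at patient level, replace the 20% sentence with:

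> The calculation is based on tissue coverage volume (14.68 vs 22 mm³, SD about 13.1 mm³ from the cited OCT sub-study). Fifty evaluable patients per group give about 79% power, at two-sided alpha 0.05, for a difference of 7.32 mm³ (33% of the EES value). Power for a 20% reduction in volume from the EES value (4.4 mm³) is about 38%.

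If a different SD or unit was used, state it and recompute these figures.

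The section should also say that the calculation is for volume and not for the primary endpoint, or restate it for mean area with its mean, SD and difference if such data exist. The 20% claim should stay only if area data support it.

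The cost is a few sentences in the Statistics section and one confirmation by the sponsor. Enrolment, conduct and analysis do not change; the stated sensitivity becomes less favourable.
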